## Appendix C Criteria for Identifying Potentially Clinically Important Laboratory Values

Analyte	Conventional Unit	Low PCI Criteria	High PCI Criteria
Hematology (whole blood)			
Hemoglobin (Male)	g/dL	<11	>17
Hemoglobin (Female)	g/dL	<10	>17
Hematocrit (Both)	%	<30	>50
Leukocyte (White Blood Cell Count)	× 10  /uL	≤2.8	≥15
Neutrophils	× 10  /uL	≤1.5	No upper limit
Eosinophils	%	≥10%	No lower limit
Platelet Count	× 10  /uL	≤75	≥700
Chemistry (serum or plasma)			
ALT (SGPT)	U/L	No lower limit	≥3 × ULN
AST (SGOT)	U/L	No lower limit	≥3 × ULN
Gamma-Glutamyl Transferase (GGT)	U/L	No lower limit	≥3 ULN
Lactate Dehydrogenase (LDH)	U/L	No lower limit	≥3 × ULN
Alkaline Phosphatase	U/L	No lower limit	≥3 × ULN
Total Bilirubin	mg/dL	No lower limit	≥1.5 ULN
CPK	mg/dL	No lower limit	≥3 ULN
BUN	mg/dL	No lower limit	≥30.0
Serum Creatinine	mg/dL	Not Applicable	>1.5 ULN
Sodium	mEq/L	≤125	≥155
Potassium	mEq/L	≤3.0	≥5.5
Calcium, total	mg/dL	<8.0	>11.0
Chloride	mEq/L	≤85	≥120
Phosphorous, inorganic	mg/dL	≤1.0 mg/dL	≥4.5 mg/dL
Magnesium	mEq/L	≤0.7 mEq/L	≥5.0 mEq/L
Uric acid	mg/dL	No lower limit	≥8.5
Albumin	g/dL	≤2.6	≥6.0
Total Protein	g/dL	≤5.0	≥10.0
Glucose (random)	mg/dL	≤45.1	≥115.0
Hb1Ac	%	No lower limit	≥7%
Total Cholesterol, Fasting	mg/dL	No lower limit	≥240 mg/dL
Urinalysis			
Blood (occult blood)		Not Applicable	≥ Moderate
Protein	mg/dL	Not Applicable	≥100 mg/dL
Glucose	mg/dL	Not Applicable	≥500 mg/dL

Abbreviations: ALT (SGPT)=alanine aminotransferase (serum glutamic-pyruvic transaminase);

AST (SGOT)=aspartate aminotransferase (serum glutamic-oxaloacetic transaminase); BUN=blood urea nitrogen; CPK=creatine phosphokinase; HbA1c=glycosylated hemoglobin; PCI=potentially clinically important; ULN=upper limit of normal.

## Appendix D Criteria for Potentially Clinically Important ECG Values

ECG Parameter	High PCI Criteria
QRS Interval	≥120 ms
PR Interval	≥220 ms
QTcB	>500 ms
QTcF	>500 ms
QTcB: change from baseline	>60 ms
QTcF: change from baseline	>60 ms

Abbreviations: ECG=electrocardiogram; PCI=potentially clinically important; PR interval=PR interval on ECG;  
QRS interval=QRS interval on ECG; QTcB=corrected QT interval using Bazett's correction method;  
QTcF=corrected QT interval using Fridericia's correction method; QRS interval=QRS interval on ECG.

**Appendix E Criteria for Identifying Additional ECG Measurements of Potential Clinical Relevance. To be Used for Medical Monitoring Purposes**

	Variable	Criterion Value a	Change Relative to Baseline
Rate			
	Tachycardia	$\geq 120$ bpm	increase of $\geq 15$ bpm
	Bradycardia	$\leq 50$ bpm	decrease of $\geq 15$ bpm
Rhythm			
	Sinus tachycardia b	$\geq 120$ bpm	increase of $\geq 15$ bpm
	Sinus bradycardia c	$\leq 50$ bpm	decrease of $\geq 15$ bpm
	Supraventricular premature beat	all	not present - present
	Ventricular premature beat	all	not present - present
	Supraventricular tachycardia	all	not present - present
	Ventricular tachycardia	all	not present - present
	Atrial fibrillation	all	not present - present
	Atrial flutter	all	not present - present
Conduction			
	1st atrioventricular block	PR $\geq 0.20$ second	increase of $\geq 0.05$ second
	2nd atrioventricular block	all	not present - present
	3rd atrioventricular block	all	not present - present
	Left bundle-branch block	all	not present - present
	Right bundle-branch block	all	not present - present
	Pre-excitation syndrome	all	not present - present
	Other intraventricular conduction block	QRS $\geq 0.12$ second	increase of 0.02 second
Infarction			
	Acute or subacute	all	not present - present
	Old	all	not present - present
ST/T Morphological			$\geq 12$ weeks post trial entry
	Myocardial Ischemia	all	not present - present
	Symmetrical T-wave inversion	all	not present - present
	Increase in QTc	QTc	
		$\geq 450$ ms (males)	$\geq 10\%$ increase
		$\geq 470$ ms (females)	

a In order to be identified as potentially clinically relevant, an on-treatment value must meet the “Criterion Value” and also represent a change from the subject’s baseline value of at least the magnitude shown in the “Change Relative to Baseline” column.

b No current diagnosis of supraventricular tachycardia, ventricular tachycardia, atrial fibrillation, atrial flutter, or other rhythm abnormality.

c No current diagnosis of atrial fibrillation, atrial flutter, or other rhythm abnormality.

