### **1.3.2 Phase 1 Study in Adolescents With Psychiatric Disorders**

The PK profile of pimavanserin was evaluated in a Phase 1, open-label, multiple ascending dose (10, 20, or 34 mg) study in adolescents (male or female adolescents between 13 and <18 years) with psychiatric disorders (ACP-103-050). When adjusted for weight at Baseline, pimavanserin steady state systemic exposure was approximately dose proportional over the studied dose range (10 to 34 mg). There were no consistent differences in pimavanserin or N-desmethyl-pimavanserin, major metabolite of pimavanserin (AC-279)  $C_{max-ss}$  and  $AUC_{\tau}$  between the age subsets; however, small differences observed were likely due to weight and not age.

Accumulation of pimavanserin (approximately 3- to 5-fold overall) and AC-279 (approximately 13- to 18-fold) is consistent with adults and was expected based on the known respective half-lives (57 hours and 200 hours) relative to dosing interval. The parent (pimavanserin) to metabolite (AC-279) steady state ratio for  $C_{max-ss}$  and  $AUC_{\tau}$  was comparable across dose cohorts and ranged from 120% to 151%. These values are comparable to those in adults confirming the lack of difference in metabolism between adults and adolescents.

Additional information on previous pimavanserin clinical studies is provided in the pimavanserin Investigator's Brochure and in the US package insert for NUPLAZID® (pimavanserin) for oral use.

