### **1.4.1 Rationale for Study Design**

This protocol describes an open-label extension study to determine the long-term safety and tolerability of pimavanserin for the treatment of irritability associated with ASD. The study follows a 6-week, Phase 2, dose ranging, randomized, double-blind, placebo-controlled study in pediatric patients (5 through 17 years of age) with a diagnosis of ASD will evaluate the efficacy, safety, and tolerability of pimavanserin by dose level (high pimavanserin dose and low pimavanserin dose).

While the focus of the double-blind study is to assess the efficacy of selected doses of pimavanserin versus placebo, evaluate the overall clinical benefit in various symptom domains

and functioning, and obtain short-term safety and tolerability data, the purpose of this open-label extension is to obtain long-term information on the safety and tolerability of pimavanserin in children and adolescents. Exploratory information about the sustained efficacy of pimavanserin will also be collected in the efficacy assessments throughout the study. The primary endpoint is treatment-emergent adverse events (TEAEs).

Examining pimavanserin long-term safety, tolerability, and efficacy is of critical importance to eventually help clinicians make an informed decision on pharmacotherapy for patients.

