#### *Rationale for dosing periods*

To ensure safe rollover of those subjects previously on placebo and minimize the risks of potential unblinding all eligible subjects will receive pimavanserin “low dose” for the first two weeks of the study. Subjects who were on “**CCI** dose” during the antecedent double-blind study will likely experience **CCI** efficacy during this period, due to the long half-life of pimavanserin, and having achieved steady state by the end of the antecedent double-blind study. At the Week 2 visit, the dose may be increased to pimavanserin “high dose”, based on the Investigator’s assessment of clinical response.

After the Week 2 visit, and up to and including the Week 20 visit, dose adjustments, either increases or decreases, may be made at any clinic visit (scheduled or unscheduled), based on the Investigator’s assessment of clinical response and tolerability.

No further dose adjustments are allowed after the Week 20 visit.

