### 3 STUDY DESCRIPTION

#### 3.1 Overview of Study Design

This study will be conducted as a 52-week, open-label extension study of the antecedent double-blind study to determine the long-term safety and tolerability of pimavanserin for the treatment of irritability associated with ASD in children and adolescents (5 through 17 years old at the time of enrolling into the antecedent double-blind study). Approximately 60 global sites and approximately eight countries will participate in this study.

The duration of participation for individual study subjects will be up to approximately 56 weeks. The total duration of exposure to pimavanserin may be greater than 52 weeks (e.g., up to 58 weeks) as some subjects have been treated with pimavanserin in an antecedent double-blind study.

The study will have two periods:

- Open-label treatment period (52 weeks)
- Safety follow-up period (at least 30 days)

Subjects who have completed the antecedent double-blind study and who have shown no significant worsening of symptoms at the end of the study as evidenced by the CGI-I of irritability will be included in this long-term extension study.

Study ACP-103-070 subjects must be consented prior to the procedures being performed at the End of Treatment (EOT) visit in the antecedent double-blind study. Procedures performed at the EOT visit of the antecedent double-blind study will be carried over to the ACP-103-070 study to be included as baseline information, and this visit will be considered the Baseline Visit (Visit 1) of the ACP-103-070 study.

The study start date is defined as the date the first subject is enrolled, which is the baseline visit date for the first subject for this open-label study.

The primary completion date is the last date that subject data was collected for the primary outcome measure.

The study completion date (End of Study) is defined as the last date that subject data was collected, which includes the safety follow-up telephone call visit. Procedures for when a subject is lost to follow-up are provided in [Section 4.6](#).

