### ***Medical Criteria***

6. Has developed a serious and/or unstable psychiatric, neurologic, cardiovascular (e.g., long QT syndrome, torsade de pointes, unstable cardiac syndrome or syncope, congestive heart failure, ongoing uncorrected hypokalemia or hypomagnesemia, non-sustained or sustained ventricular tachycardia), respiratory, gastrointestinal, renal, hepatic, hematologic, or other medical disorder, including cancer or malignancies that, in the judgment of the Investigator, would jeopardize the safe participation of the subject in the study, or has major surgery planned during the study
7. Has experienced any change in medical or treatment status that may increase the risk associated with taking pimavanserin, would interfere with safety assessments, or would confound the interpretation of study results, based on the Investigator's judgment
8. For age <13 years, a resting position (sitting or supine) systolic (SBP) and/or diastolic blood pressure (DBP) level  $\geq$ 90th percentile for gender-specific age and height charts from the National Heart and Lung Institute (NHLI), at Baseline. For age  $\geq$ 13 years a resting position (sitting or supine) SBP  $\geq$ 120 mmHg and/or a DBP  $\geq$ 80 mmHg, at Baseline.
9. Has a clinically significant abnormal ECG at Baseline or any of the following cardiac conduction abnormalities:
  - a. Corrected QT interval using Fridericia's correction method (QTcF)  $\geq$ 450 ms
  - b. PR interval on ECG  $>$ 220 ms
  - c. Evidence of second- or third-degree atrioventricular block
  - d. Evidence of complete left bundle branch block
  - e. Intraventricular conduction delay with QRS interval on ECG (QRS)  $>$ 110 ms
  - f. QRS or T wave morphology that could, in the Investigator's opinion, render QT interval assessment unreliable
  - g. Sick sinus syndrome
  - h. Non-sinus rhythm
  - i. Resting heart rate  $<$ 50 beats per minute

One repeat set of triplicate ECGs is allowed at Baseline.

10. Weight  $<$ 15 kg
11. *In Italy only:* Has a sensitivity to any compound present in pimavanserin or any metabolites or compounds listed in the Investigator's brochure as being present in this medication

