### **5.1.3 Dosing and Administration**

At the Baseline visit of Study ACP-103-070, study drug will be dispensed to the subject to take home. The subject and their parent/LAR will be provided instructions for the subject's first dose of study drug on the day after the Baseline visit.

Each daily dose consists of one capsule. Subjects should be instructed to take one capsule, orally, once daily, in the morning, at the same time every day. Subjects should be instructed to not to open the capsules. The capsules may be taken with or without food.

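### For children rolling over from pimavanserin, the QTcF change categories and >60 ms counts start from an on-drug baseline, and the plan does not clearly extend its second, drug-free baseline to them

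*Protocol*

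**What the plan says.** **Which ECG is the baseline.** Protocol 3.1 says that procedures from the antecedent end-of-treatment visit "will be carried over to the ACP-103-070 study to be included as baseline information". Protocol 5.1.3 places the "first dose of study drug on the day after the Baseline visit". SAP 5.3.2 takes the last non-missing value before open-label dosing.

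**Drug status at that visit.** Protocol 1.4.1: "The study follows a 6-week, Phase 2, dose ranging, randomized, double-blind, placebo-controlled study in pediatric patients". Protocol 1.3.2 describes accumulation of drug and metabolite as "expected based on the known respective half-lives (57 hours and 200 hours) relative to dosing interval". Protocol 1.4.2, on dosing periods, refers to children from one (redacted) dose group as "having achieved steady state by the end of the antecedent double-blind study".

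**What is counted from it.** Appendix D flags a QTcB or QTcF change above 60 ms, and SAP Table 6 counts the same change. SAP 14.4 tabulates QTcF change as ≤10, 11 to 30, 31 to 60 and >60 ms, by visit and for the post-baseline maximum. Appendix E, for medical monitoring, states in its footnote a: "In order to be identified as potentially clinically relevant, an on-treatment value must meet the" criterion value, here a QTc of at least 450 ms (males) or 470 ms (females). It also needs a change of at least 10% from the child's "baseline value of at least the magnitude shown in the" change column. None of these places says which baseline is meant.

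**What is not affected by baseline.** SAP 14.4 also has observed QTcF categories (≤450, 451 to 480, 481 to 500, >500 ms). Appendix D and Table 6 have an absolute limit of 500 ms.

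**The second baseline.** Protocol 9.5 and SAP 5.1.1 present change for every continuous safety and efficacy measure from the antecedent baseline as well. The SAP labels this presentation exploratory.

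**Entry.** Exclusion 9 reads "Has a clinically significant abnormal ECG at Baseline or any of the following cardiac conduction abnormalities", and its list begins with QTcF of 450 ms or more.

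**The concern.** Protocol 1.5.1 reports dose-related QTc prolongation in adolescents given pimavanserin with other psychotropics. Long-term safety is the primary objective, and protocol 9.5.2 promises a categorical analysis of QTc change. For pimavanserin rollovers, those categories measure change from a value that may already contain the effect they are meant to show. A child from the antecedent high-dose arm also restarts on the low dose (protocol 3.1.1), so the early changes follow a step down. A reader of the category table could conclude that few children had a sizeable QTcF rise on pimavanserin, when part of the rise sits in the baseline.

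**Working it through.** The plan gives no figure on this point. Its one computed figure is the Rule of Three bound, 3/193 = 1.55%, which reproduces the stated 1.6%. It matters here only as the source of N = 193.

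**1. Is the baseline on drug?** Six weeks is 42 × 24 = 1,008 h. The fraction of steady state is 1 − 2^(−t/half-life):
- drug: 1 − 2^(−1008/57) = above 99.9%
- metabolite: 1 − 2^(−1008/200) = 97.0%

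Dosing resumes the next day, so the answer is yes.

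**2. What happens to a change limit?** If d ms of drug effect is already in the baseline, a rise above 60 ms from that baseline is a rise above 60 + d from the drug-free value. For assumed d of 5, 10, 15 and 20 ms, the limit becomes 65, 70, 75 and 80 ms. The documents do not give d.

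**3. One-visit check on the categories.** Assume a total effect of 20 ms and an SD of change of 15 ms, with normal changes.

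| Effect already in baseline | P(change >30 ms) | P(change >60 ms) |
|---|---|---|
| 0 ms | 25.2% | 0.38% |
| 10 ms | 9.1% | 0.04% |
| 20 ms | 2.3% | 0.003% |

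**4. Expected numbers of children.** If the antecedent arms were 1:1:1 (ratio not given), 193 × 2/3 ≈ 129 children have an on-drug baseline. Further assumptions are a drug-free QTcF mean of 405 and SD of 18 ms, a shift of 5 to 15 ms, a within-child SD of 8 to 14 ms, and the highest of the 8 post-baseline visits. Either all rollovers carry the full shift at baseline, or half of them carry 55% of it. Simulation (1,000,000 draws) gives, of 129:

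| Change | From open-label baseline | From antecedent baseline |
|---|---|---|
| >30 ms, range | 3 to 47 | 10 to 80 |
| >30 ms, middle setting | 17.1 | 40.1 |
| >60 ms, range | 0 to 2.1 | 0 to 8.4 |
| >60 ms, middle setting | 0.03 | 0.18 |

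The middle setting is a 10 ms shift, SD 10 ms, and half the rollovers carrying 55%. There the open-label >30 ms count is 17.1/40.1 = 43% of the other. Over the whole range it is 8% to 78%.

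**5. Example.** Take a girl with QTcF 400 ms drug-free, 415 ms at open-label baseline (assumed) and 462 ms on treatment. Her change is 462 − 400 = 62 ms from drug-free, but 462 − 415 = 47 ms (47/415 = 11.3%) from the open-label baseline. She is tabulated in 31 to 60 ms, and the QTcF >60 ms count misses her.

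Whether Appendix E flags her depends on which QTc it means. QTcB = QTcF × (HR/60)^(1/6), so her QTcB reaches 470 ms at HR = 60 × (470/462)^6 = 66.5 bpm. At an unchanged 75 bpm her QTcB goes from 430.7 to 479.5 ms, still an 11.3% rise, and both Appendix E conditions are met.

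**6. Appendix E's combined rule.** The first flag is at max(450 or 470, 1.10 × baseline). It is flat up to a baseline of 450/1.10 = 409 ms (boys) or 470/1.10 = 427 ms (girls), then rises: 440 → 484 ms, 449 → 493.9 ms. In a further simulation over assumed distributions, which counted Appendix D's QTcB rows as well as the QTcF rows, at most about 0.4 of 193 children exceeded 480 ms with no flag.

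**The case against.** The strongest reply is that the plan already covers this. Protocol 9.5 and SAP 5.1.1 set a general rule that changes are shown from both baselines. QTcF is a continuous measure, and the table specifications are in a separate document. A reader might infer that the plan ignores the drug-free baseline; it does not. What stands is narrower. The rule is worded for continuous measures, whereas the categories and Table 6 are counts of children, and nothing says the rule reaches them.

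Second, SAP 14.4 uses cohort denominators, and SAP 13.1 defines cohorts by double-blind arm. Placebo rollovers, with a drug-free baseline, therefore appear beside the pimavanserin cohorts. This helps interpretation but does not correct the pimavanserin cohorts' counts. It is also fair that the antecedent study covers the first six weeks and that change from open-label baseline answers the extension's own question. That argues for keeping the present count, not against adding the other.

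Third, other safeguards exist. Observed 481 to 500 ms is tabulated, 500 ms is an absolute limit, every ECG is read by a clinician and centrally (protocol 6.4.3), and the antecedent-baseline continuous tables show the largest change at each visit. With less than one child expected above 60 ms in the middle setting, that maximum already says much. Protocol 1.1.3 also calls the QTc effect minimal at the maximum dose, on adult data.

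Two stronger readings are tempting. One is that the girl in the example would trigger no flag at all up to about 96 bpm, the rate at which her QTcB would pass 500 ms. Appendix E says QTc without naming a correction, and SAP 14.4 takes QTc to include QTcB. On that reading she goes unflagged only below about 67 bpm. The other is that Appendix E's rising limit is a serious gap. The arithmetic is right, but pairing a level with a rise is a defensible screen, and the expected number missed is below one child.

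**Conclusion.** The concern holds in a limited form and is minor. For pimavanserin rollovers, the SAP 14.4 change categories and the >60 ms counts understate change from the drug-free state by the effect already present, and the plan does not clearly apply its second baseline to them. The direction follows from the documents for any positive QTc effect at baseline.

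The size does not follow from the documents. It rests on an assumed shift, variability, QTcF distribution and arm ratio. It may be material for changes above 30 ms, where the middle setting loses more than half the count. For changes above 60 ms the middle setting involves less than one child on either baseline. This is a gap in derivation and wording; the documents do not support reading it as an absence of QTc monitoring.

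**What to change.** In SAP 14.4 and Table 6, state that the QTcF change categories and the >60 ms counts are also given from the antecedent-study baseline, by cohort, beside those from the open-label baseline. Apply the Appendix D and E change limits from both baselines too. Each child's own earlier ECG is used whatever the arm, so flagging needs no unblinding.

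The cost is one derived variable and a few lines of text. The antecedent ECGs should already be held, because SAP 5.1.1 uses that baseline. The SAP change carries most of the benefit; the appendix wording is a protocol modification that goes to the ethics committees under protocol 10.7. The downside is extra flags, about 0 to 8 children above 60 ms from the antecedent baseline under the assumptions above, some of them visit-to-visit noise.

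Do not restrict the Appendix E row to QTcF, since that would remove the QTcB route and narrow the screen. A flag for any QTcF above 480 ms whatever the change is optional. It would add about 0 to 3 children, and the gap it closes is expected to be below one child.

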## Appendix F Criteria for Potentially Clinically Important Vital Signs

Vital Sign Parameter	Unit	Criteria		
		Observed Value	And/Or	Change Relative to Baseline
Systolic blood pressure (supine or sitting)	mmHg	≥140	And	Increase of ≥20
		≤70	And	Decrease of ≥20
Diastolic blood pressure (supine or sitting)	mmHg	≥90	And	Increase of ≥15
		≤50	And	Decrease of ≥15
Pulse (supine or sitting)	bpm	≥120	And	Increase of ≥15
		≤50	And	Decrease of ≥15
Weight	kg	Not Applicable		Increase of ≥7%
				Decrease of ≥7%

## Appendix G Syncpe Adverse Event Questions

## Appendix H Somnolence Adverse Event Questions

Horizontal bar chart showing CCI values for 15 categories. The categories are listed on the y-axis, and the x-axis represents the CCI value, ranging from 0 to 100. Most categories have a CCI value of 100, except for one which is approximately 20.

Category	CCI
1	100
2	100
3	100
4	100
5	100
6	100
7	100
8	100
9	100
10	100
11	100
12	100
13	100
14	100
15	20

DSMB	data and safety monitoring board
ECG	electrocardiogram
eCRF	electronic case report form
EDC	electronic data capture
eGFR	estimated glomerular filtration rate
ESRS-A	Extrapyramidal Symptom Rating Scale–Abbreviated
ET	early termination
EOT	end of treatment
GSD	Guidance for Site Documentation and Data Management Querying of Data Impacted by COVID-19
HbA _{1c}	glycosylated hemoglobin
IQ	intelligence quotient
MedDRA	Medical Dictionary for Regulatory Activities
Msec	milliseconds
PCI	potentially clinically important
QRS	QRS interval of ECG
QT	QT interval for heart rate of ECG
QTc	corrected QT interval of ECG for heart rate
QTcB	corrected QT interval using Bazett’s correction method
QTcF	QT interval corrected for heart rate using Fridericia’s formula
RBS-R	Repetitive Behavior Scale–Revised
SAE	serious adverse event
SAP	statistical analysis plan

Terms	Definitions
SD	standard deviation
SE	standard error
SOC	system organ class
TEAE	treatment-emergent adverse event
ULN	upper limit of normal
US	United States
VABS	Vineland Adaptive Behavior Scales

